3.3.3 Deep Venous Thrombosis

If deep venous thrombosis (DVT) or pulmonary embolus (PE) or other grade 3 or 4 clotting event occurs, at the discretion of the treating investigator, therapy will be initiated with full dose Low Molecular Weight Heparin or other anticoagulants as indicated.. If recurrent DVT or PE occurs despite full and therapeutic anticoagulation, therapy with flavopiridol must be terminated and the patient will be removed from the protocol.

3.3.4 Pulmonary Reactions

Patients who develop grade 2 or 3 dyspnea with or without chest pain, temporally related to flavopiridol, will be monitored closely. Oxygen saturation and a chest x-ray should be checked. These patients may be retreated without dose reduction if the toxicity resolves completely. Patients who develop dyspnea that is temporally related to flavopiridol and is severe (at rest grade 4) or associated with tachypnea, hypoxemia, bronchospasm or pulmonary

edema/pneumonitis will be considered to have had grade 4 toxicity and will be removed from the protocol. Appropriate supportive measures including steroids and diuretics should be instituted at the discretion of the treating investigator.

3.3.5 Liver Function Tests

Liver tests, including AST, ALT and total bilirubin will be checked weekly during therapy.

- In order to initiate a cycle, liver function tests must be at grade ≤ 2 .
- Within 24 hours prior to each dose, LFTs must be ≤ 2 in order for therapy to be administered.
- If liver function tests demonstrate \geq grade 3 elevation, flavopiridol will be held until resolution to ≤ 2 .
- If \geq grade 3 elevation occurred flavopiridol will be reduced by one dose level (except for patients at dose level 1 in which case flavopiridol will be discontinued).

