3.2 DRUG ADMINISTRATION

3.2.1 Phase 1 Dosing and Schedule

The Phase I dose escalation will follow one of two different escalation rates shown in Tables 1 and 2 below. If DLT is observed in 0/3 or 1/6 patients on dose level 1, subsequent patients will be enrolled according to the paradigm described in Table 1 below. If DLT is observed in 2/6 patients on dose level 1, subsequent patients will be enrolled according to the paradigm described in Table 2 below.

Flavopiridol dose levels

Table 1	Cycle 1, Week 1		Cycle 1, Weeks 2–4, AND All weeks During All Subsequent Cycles	
Dose level	Bolus x30 minutes IV	Continuous infusion x 4 hrs	Bolus x30 minutes IV	Continuous infusion x 4 hrs
1	30mg/m ²	30mg/m ²	30mg/m ²	50mg/m ²
2	30mg/m ²	50mg/m ²	30mg/m ²	50mg/m ²
3	30mg/m ²	50mg/m ²	40mg/m ²	60mg/m ²
4	40mg/m ²	60mg/m ²	40mg/m ²	60mg/m ²

Table 2	Cycle 1, Week 1	Cycle 1, Weeks 2–4, AND All weeks During All Subsequent Cycles

Dose level	Bolus x30 minutes IV	Continuous infusion x 4 hrs	Bolus x30 minutes IV	Continuous infusion x 4 hrs
1	30mg/m ²	30mg/m ²	30mg/m ²	50mg/m ²
1A	25mg/m ²	25mg/m ²	30mg/m ²	50mg/m ²
1B	25mg/m ²	25mg/m ²	40mg/m ²	60mg/m ²

- Administer weekly x 4 consecutive weeks, followed by 2 weeks without flavopiridol treatment for a cycle duration of 6 weeks (1 cycle).
- For cycles 2-6, administer the doses given during cycle 1, weeks 2-4 for all doses.
- Administer up to 6 cycles if no disease progression.
- Restage all positive sites of disease after every 2 cycles, except bone marrow which should be repeated after other sites have achieved a CR.
- Administer flavopiridol in the inpatient unit on cycle 1, dose 1 (bolus and infusion).
- Unless medically contraindicated, all patients will receive allopurinol 300 mg per day on cycle 1 x 5 days. All patients should receive at least 200 mL/hr 0.9% Sodium Chloride Injection for 6 hours prior to the first flavopiridol dose. Detailed required guidelines for Tumor Lysis Syndrome prevention is shown in section 4.3.
- If cycle 1, dose 1 is tolerated without TLS, subsequent doses may be administered outpatient.

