3.2.2 Phase 2 Dosing

- Dose will be the MTD from the phase I portion.
- Administer weekly x 4 consecutive weeks, followed by 2 weeks without flavopiridol treatment for a cycle duration of 6 weeks (1 cycle).
- For all weeks of all cycles after cycle 1, patients will receive the dose administered on cycle 1, weeks 2-4.
- Administer up to 6 cycles if no disease progression.
- Restage all positive sites of disease after every 2 cycles, except bone marrow which should be repeated after other sites have achieved a CR.

3.2.3 Definition of Dose Limiting Toxicity:

Dose-limiting toxicity will be determined during the first cycle of treatment and is defined as:

- any grade 3 or greater non-hematologic toxicity excluding transient liver function abnormalities that resolve spontaneously within 10 days and/or transient electrolyte abnormalities that are not life-threatening, or fatigue
- grade 4 thrombocytopenia (< 25,000/mcL) persisting for 4 or more days

- grade 4 neutropenia ANC < 500/mcL persisting for 7 or more days despite the institution of G-CSF
- inability to continue with cycle 2 by 3 weeks after the end of cycle 1. Exceptions to this (i.e. accidents, family emergencies, etc) will be evaluated on a case-by-case basis.
- irreversible \geq grade 2 non-hematologic toxicity
- irreversible grade 3 thrombocytopenia at least possibly due to flavopiridol.
- And is a drug related event with an attribution of possible, probable or definite.

Patients with compromised bone marrow function from lymphoma will not be evaluable for hematologic related DLT. Irreversible is defined as lasting > 3 weeks. All toxicity will be evaluated and scored using NCI Common Terminology Criteria for Adverse Events (CTCAE) version 3.0 until December 31, 2010. CTCAE version 4.0 will be utilized beginning January 1, 2011.

3.3 TREATMENT MODIFICATIONS:

Patients should have recovered toxicities that are clinically significant and attributable to flavopiridol to grade 1 or baseline before beginning another cycle. If toxicity has not resolved to this level within 3 weeks from the end of the previous cycle, flavopiridol will be discontinued.

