3.3.1 Hematological Toxicity

Dose modifications of flavopiridol should be made according to the following schema:

Hematological toxicity on Day 1 of Cycle:

Platelets (at start of cycle)	Flavopiridol Dose
< 50,000	Delay up to 2 weeks until Plts \geq 50,000 and reduce dose 20%.
Neutrophil count (at start of cycle)	
< 500	Start G-CSF. Administer flavopiridol when ANC is > 500 . Once G-CSF is instituted, continue to administer it prophylactically for subsequent (days 2-6 each week) doses
< 500 despite G-CSF for 7 or more days	Reduce dose of flavopiridol by 20% and repeat dose only when ANC is > 500

Hematological Toxicity During the Cycle:

Platelets	Flavopiridol Dose
< 50,000	Delay up to 2 weeks until Plts \geq 50,000 and reduce dose 20%.
Neutrophil count	
< 500	Start G-CSF. Administer flavopiridol when ANC is > 500 . Once G-CSF is instituted, continue to administer it prophylactically for subsequent (days 2-6 each week) doses
< 500 for 7 or more days despite G-CSF	Reduce dose of flavopiridol by 20% and repeat dose only when ANC is > 500

If grade 4 neutropenia lasting for 7 or more days on G-CSF or grade 3 thrombocytopenia develops during treatment, hold the next dose until recovery below this toxicity and reduce dose by 20% for subsequent doses and cycles as instructed in above tables.

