3.3.2 Diarrhea Toxicity

Diarrhea treatment during cycle: At first loose stool: Start loperamide 2 mg p.o. q 2 h while awake and q 4 h while sleeping. Continue around the clock until 12 h diarrhea free. If diarrhea free > 12 h, stop loperamide. Lomotil may also be given for diarrhea in addition to or as an alternative to loperamide. Please note the manufacturer's recommended maximum daily dose of loperamide is 16 mg. If grade 3 diarrhea or diarrhea is accompanied by mucus or dehydration, hold doses of flavopiridol (if applicable) and hydrate.

Diarrhea Toxicity on Previous Cycle:

Diarrhea on previous cycle	Flavopiridol dose
< Grade 3	No change
Grade 3 or associated with mucus or dehydration	Reduce dose by 20% on all subsequent cycles.
Grade 4	Hold until diarrhea grade < 3 and reduce dose 20%

Diarrhea Toxicity During the Cycle:

Diarrhea on previous week	Flavopiridol dose
< Grade 3	No change
Grade 3	Reduce dose by 20%. If toxicity persists for > 7 days after reduction, hold dose.
Grade 4	Hold until diarrhea grade < 3 and reduce dose 20%

If grade 3 diarrhea on previous cycle, reduce dose 20% on subsequent cycles. If grade 4 diarrhea on previous cycle, hold until diarrhea < grade 3 and reduce dose 20%.

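### The one-level dose cut for grade 3 or higher liver elevations in section 3.3.5 gives no reduction at a first on-treatment event from level 2 or level 4, and is ambiguous at level 1A

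*Combined protocol and SAP*

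**What the plan says.** Section 3.3.5 checks liver tests weekly and within 24 hours before each dose. A grade 3 or higher elevation stops dosing until the tests are back to grade 2 or lower. On restart, "flavopiridol will be reduced by one dose level (except for patients at dose level 1 in which case flavopiridol will be discontinued".

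The dose levels are defined in Tables 1 and 2 of section 3.2.1. Each level has one bolus-plus-infusion pair for cycle 1 week 1 and another for every dose after that. Section 3.2.1 fixes the later doses: "For cycles 2-6, administer the doses given during cycle 1, weeks 2-4 for all doses". Section 3.2.2 does the same for phase II, "For all weeks of all cycles after cycle 1, patients will receive the dose administered on cycle 1, weeks 2-4", and sets the phase II dose: "Dose will be the MTD from the phase I portion".

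The other toxicity rules that lower the dose use a percentage. Section 3.3.1 says "reduce dose by 20% for subsequent doses and cycles as instructed in above tables", and section 3.3.2 says "Reduce dose by 20% on all subsequent cycles".

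**The concern.** A reduction written in dose levels lowers the dose only if adjacent levels differ in the doses still to be given. Here, some adjacent levels differ only in the very first dose. A patient at level 2 or 4 who recovers from a grade 3 or higher liver elevation would therefore restart on exactly the dose that preceded it, under a rule that says the dose goes down.

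The rule also treats equal doses unequally. A level 1 patient receiving 80 mg/m² is taken off drug, while a level 2 patient receiving the same 80 mg/m² continues unchanged. If the MTD turned out to be level 2 or 4, the ineffective step would apply throughout phase II.

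**Working it through.** **Inputs** (section 3.2.1, Tables 1 and 2; bolus + infusion, mg/m²):

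| Level | Cycle 1 week 1 | All later doses |
|---|---|---|
| 1 | 30+30 = 60 | 30+50 = 80 |
| 2 | 30+50 = 80 | 30+50 = 80 |
| 3 | 30+50 = 80 | 40+60 = 100 |
| 4 | 40+60 = 100 | 40+60 = 100 |
| 1A | 25+25 = 50 | 30+50 = 80 |
| 1B | 25+25 = 50 | 40+60 = 100 |

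**Step 1: the effect of one level down.** An on-treatment elevation follows dose 1, so only the last column matters. Change = (later dose one level down ÷ later dose now) − 1.

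- 4 to 3: 100/100 − 1 = 0%
- 3 to 2: 80/100 − 1 = −20%
- 2 to 1: 80/80 − 1 = 0%
- 1B to 1A: 80/100 − 1 = −20%
- 1A: no lower level is defined in Table 2. If level 1 is taken as the next level, 80/80 − 1 = 0%.

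The week 1 dose does fall for 4 to 3 (100 to 80) and 2 to 1 (80 to 60). That would help only if the elevation came before any drug was given.

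**Step 2: successive events under the present rule.** Later dose before any event, then after each event:

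- Level 1: 80, stop
- Level 2: 80, 80, stop
- Level 3: 100, 80, 80, stop
- Level 4: 100, 100, 80, 80, stop
- Level 1A: 80, then ambiguous
- Level 1B: 100, 80, then ambiguous

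**Step 3: does another rule supply the missing cut?** Section 3.2.3 keeps some liver events out of the DLT definition, "excluding transient liver function abnormalities that resolve spontaneously within 10 days", so for those section 3.3.5 is the specific dose rule. For liver events that do count as DLTs, I found no general rule that lowers the dose after a DLT. Section 3.3 requires clinically important drug-related toxicity to return to grade 1 or baseline before a new cycle, and stops drug if that takes more than 3 weeks from the end of the last cycle. That governs when drug restarts, not how much is given.

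**Step 4: size per dose, against a 20% cut.** Level 2: 0.8 × 80 = 64, a difference of 16 mg/m². Level 4: 0.8 × 100 = 80, a difference of 20 mg/m². The upper bound is an event after dose 1, all remaining doses given and no second event. There are 6 × 4 − 1 = 23 such doses, so 23 × 16 = 368 and 23 × 20 = 460 mg/m².

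**Step 5: patients affected.** The documents give no rate of grade 3 or higher liver events. Section 8.4 lists ALT, AST and bilirubin increases in its band of 20% or less, without grades. Assume 2%, 5% or 10%, and that the MTD is level 2 or 4. If both arms reach stage two, section 6 counts 44 + 6 = 50 patients, which gives 1, 2.5 or 5. With the 70% early stopping that section 6 gives at a 20% response rate, the expected number is 2 × (14 + 0.3 × 11) = 34.6, which gives about 0.7, 1.7 or 3.5.

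**The case against.** The best defence is that section 3.3.5 works, in effect, as one monitored rechallenge. Drug is held until recovery, tests are repeated before every dose, recovery between cycles must be to grade 1 or baseline, and the investigator may withdraw a patient (section 3.5). A second event stops drug from level 2 and cuts it to 80 from level 4. This stands as a limit on harm. It does not make the first step a reduction, which is what the text orders.

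A reader might try to settle intent from section 3.3.4, which says of some pulmonary events "These patients may be retreated without dose reduction if the toxicity resolves completely", and infer that full-dose retreatment is meant only where it is stated. The documents do not support that: section 3.3.7 resumes drug after certain grade 3 or higher events with no cut and no such statement. The point rests on the word for reduction in section 3.3.5 itself.

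A reader might also infer that level 1A has no rule at all. It is the lowest level of Table 2 and is labelled as a variant of level 1, so discontinuation is a natural reading. It is also the cautious one. The text does not say so, which makes this an ambiguity, and one that arises only if Table 2 is used, after 2 of 6 patients have DLT at level 1.

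The cumulative figures should not be read as typical harm. A patient who reaches them has taken every planned dose without a second event. Finally, the 20% figure comes from rules for other toxicities, and nothing in the documents shows that it is specific to the liver. It does equal the 100 to 80 step that section 3.3.5 already produces from levels 3 and 1B.

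**Conclusion.** The point holds. At a first on-treatment event the ordered reduction is 0% from levels 2 and 4, is a real 20% from levels 3 and 1B, is discontinuation at level 1, and is ambiguous at level 1A. This follows from the dose tables and needs no assumption beyond the event coming after dose 1.

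The consequence is modest: 16 or 20 mg/m² more per later dose than under a 20% cut, with 368 and 460 mg/m² as upper bounds only. The patient counts rest on assumed event rates and on the MTD being level 2 or 4; counts based on 50 patients also require both arms to complete stage two.

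A reader might infer that the MTD or the phase II conclusions are compromised. The documents do not support that: the DLT definition, the escalation rule and the response boundaries do not depend on this sentence. It is a safety instruction that should be corrected. Sections 5.2 and 8.3 record the protocol as completed with CTEP, so the practical gain depends on whether patients are still being dosed.

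**What to change.** In section 3.3.5:

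- For levels 2, 3, 4 and 1B, replace the one-level step with a 20% reduction of the current bolus and infusion, for all later doses. That takes 30+50 to 24+40 (80 to 64) and 40+60 to 32+48 (100 to 80).
- Keep discontinuation at level 1 and state that it also covers level 1A.
- Discontinue at a further grade 3 or higher event in any patient already reduced from 80 mg/m².

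The sequences become: level 2, 80, 64, stop; levels 3, 4 and 1B, 100, 80, 64, stop; levels 1 and 1A, 80, stop. At levels 1 to 4 no step is less cautious than now. At level 1B, a stop at the second event is one reading of the present text, so the clinical team should confirm the extra step to 64. They should also confirm that 20% suits liver events.

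The change is a few lines of text, with no added visits, tests or patients. The price is lower dose intensity in those affected. Under the assumed 2% to 10% event rates, the mean dose falls by at most 0.02 × 20% = 0.4% to 0.10 × 20% = 2%, and 0.5 to 2.5 of 25 patients per full arm would be treated below the MTD.

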3.3.6 Tumor Lysis Syndrome

Tumor lysis syndrome is a term given to a group of metabolic complications that occur after treatment of neoplasms. These disorders include hyperkalemia, hyperphosphatemia, hyperuricemia, hypocalcemia and acute renal failure. Due to cases of tumor lysis syndrome encountered by Byrd et al, that have included two early fatal events associated with uncontrolled hyperkalemia, the following supportive care issues are required for patients on cycle 1 dose 1 who are participating on this trial. These serve as guidelines for management that can be modified to facilitate good patient care based upon the individual being treated.

- 1) Primary decisions regarding management of tumor lysis syndrome and cytokine release syndrome will be made by the principal investigator or designees. Only one patient will be initiated on flavopiridol per day to assure adequate monitoring and intervention can be provided.
- 2) Patients will be admitted to the in-patient service the evening prior to scheduled doses of flavopiridol, for a minimum of the first treatment (cycle 1 dose 1). Patients who do not have significant tumor lysis may receive cycle 1 doses 2-4 as well as all subsequent cycles as outpatients. This will allow inpatient monitoring of patients during the most critical window of vulnerability to tumor lysis, yet allow patients who tolerate flavopiridol to eventually be treated in the outpatient setting.
- 3) The Renal consult service will be made aware of all inpatient admissions for treatment on this study. Administer flavopiridol only during hours of the day when the renal service has been notified and is prepared to perform dialysis within 1 hour of notification.
- 4) Patients will receive IV hydration with 5% dextrose infusion with 200 mEq (200 mmol) sodium bicarbonate per Liter at 200 mL/hr for at least 10 hours prior to initiation of flavopiridol dose. This alkaline infusion will continue throughout the course of therapy and for at least 10 hours after completion of infusion.
- 5) Patients will begin allopurinol 300 mg orally per day at least 24 hours before cycle 1 dose 1 and continuing for at least 1 week. Rasburicase may be administered at the discretion of the treating physician but should be reserved for patients whose uric acid rises to 10 or above despite prophylaxis with allopurinol and hydration. If rasburicase is used, uric acid measurements must be drawn in a heparinized tube, placed on ice immediately and transported for rapid analysis to avoid spuriously low results.

- 6) Patients will receive an oral phosphate binder (Calcium Acetate 1334 mg or equivalent) the evening prior to and in the morning prior to initiation of the flavopiridol bolus.
- 7) Patients will have potassium levels drawn the morning within 3 hours prior to initiation of flavopiridol (with the investigator knowing the value prior to starting therapy); at the end of the bolus infusion, hourly during administration of flavopiridol; and 1, 2 and 3 hours after completion of flavopiridol dose. These tests will be performed STAT. Patients with serum potassium \geq 4.0 will receive a 30 gm dose of sodium polystyrene sulfonate P.O. prior to initiation of the flavopiridol bolus.
- 8) Patients will continue to receive Flavopiridol as outlined in the protocol (Section 4.2).
- 9) Patients who develop clinical evidence of cytokine release syndrome or who have hyperkalemia requiring dialysis will receive immediate steroid therapy with an equivalent of at least 20 mg of IV dexamethasone. Cytokine syndrome is described in the CTCAE Version 3.0. It occurs during or shortly after drug infusion and generally resolves within 24 hours after completing the infusion. The signs and symptoms of cytokine syndrome include allergic reaction (including drug fever), arthralgia, bronchospasm, cough, dizziness, dyspnea, fatigue, headache, hyper- or hypotension, myalgia, nausea, pruritis, rash, rigors, chills, sweating, tachycardia, tumor pain, or urticaria.
- 10) Patients who develop a rise in their serum potassium to more than 4.5 mmol/L should immediately receive a 30 gm dose of sodium polystyrene sulfonate P.O..
- 11) Patients who develop a rise in their serum potassium to more than 5.0 mmol/L will receive a 10 unit dose of IV insulin and 50mL of 50% dextrose injection. (Prior to this intervention, it is permissible to repeat this measurement if hyperkalemia is suspected to be due to specimen hemolysis). If there is true hyperkalemia, drug administration should be discontinued.
- 12) Patients who develop a rise in their serum potassium to more than 5.5 will be considered for emergent intermittent or continuous hemodialysis. Prior to this intervention, it is permissible to repeat this measurement if hyperkalemia is suspected to be due to specimen hemolysis.
- 13) Patients who develop cytokine release (defined in 9) or who require dialysis for hyperkalemia and/or other symptoms of tumor lysis will be administered prophylactic antibiotics for Gram negative organisms (piperacillin sodium 4 gm + tazobactam sodium 0.5 gm Q8 hours or equivalent) and Gram positive organisms (vancomycin 1 gm IV Q12 hours or equivalent) until dialysis is discontinued.
- 14) Patients may be discharged home the day after the flavopiridol dose has been given, and their chemistry laboratory results have been reviewed by the treating physician.
- 15) For patients who have been initially treated for TLS, the decision about when it is safe and feasible to move them to the outpatient setting will be made by the responsible investigator. If during outpatient therapy severe tumor lysis develops requiring hemodialysis, the patient will not be retreated with flavopiridol.
- 16) Patients receiving flavopiridol in the outpatient clinic will begin alkaline IV hydration (similar to point 4) beginning at least 1 hour prior to initiation of the study drug. This alkaline infusion will continue throughout the course of therapy and for at least 2 hours following completion of infusion.
- 17) For patients who have been treated for TLS during the first cycle, a single dose of dexamethasone 20 mg PO should be administered for all further doses at the discretion of the investigator to diminish risk of cytokine release syndrome.

- 18) Patients will continue to take allopurinol and an oral phosphate binder, as above unless they become intolerant to it.
- 19) During dose 2, the potassium levels will be obtained as outlined in item 7 of section 4.3.6. Following completion of dose 2, patients will have potassium levels drawn prior to, every 2 hours during, and after completion of the flavopiridol dose in the outpatient setting. Intervention with sodium polystyrene sulfonate and/or IV insulin will be as above. Patients will not be discharged from the outpatient unit with an elevated serum potassium; if necessary, patients must be admitted overnight for observation.
- 20) Telemetry monitoring will be performed at the discretion of the PI or his designee.

